1 BACKGROUND

ITP is the most common autoimmune cytopenia in children, and causes an often severely reduced platelet count, variable bleeding symptoms, and health-related quality of life (HRQoL) reductions due to factors such as activity restrictions, frequent medical visits and interventions, and fatigue.¹⁻³ In an era when the fields of hematology and immunology are advancing rapidly with the development of drugs targeted to specific disease mechanisms, the treatment of newly diagnosed ITP remains primitive and non-specific, with no novel therapies introduced in the past 30 years.⁴

Eltrombopag is an oral, small-molecule, nonpeptide thrombopoietin-receptor agonist (TPO-RA). The drug initiates thrombopoietin-receptor signaling by interacting with the transmembrane domain of the receptor, thereby inducing proliferation and differentiation of cells in the megakaryocytic lineage. Eltrombopag is a drug that has the potential to change the landscape of newly diagnosed ITP for both children and adults. While there are myriad drugs available to choose amongst for treatment of chronic ITP, including immunosuppressants and thrombopoietin receptor agonists, the treatment of newly diagnosed ITP is generally limited to three first-line medications: corticosteroids, intravenous immunoglobulin (IVIG), and anti-D globulin. Each of these agents has either undesirable side effects, undesirable logistics of administration, or both. Additionally, each of these agents acts only transiently to raise the platelet count, and in children with continued active ITP, the platelet count will decrease days to weeks after the medication is given. As a once daily, non-immunosuppressant, oral agent, eltrombopag offers the possibility of a sustained platelet response over weeks to months with continued use. This could result in improved HRQoL and reduction in fatigue, as well as other benefits.⁵

Eltrombopag is an established therapy for pediatric patients with chronic ITP. Safety and efficacy were established in the PETIT⁶ and PETIT2⁷ trials, and the drug was FDA-approved for children with chronic ITP in 2015.

Off-label use for adults with newly diagnosed ITP has been described in two small single-center trials. A single-arm study of dexamethasone in combination with 4 weeks of eltrombopag used upfront in adult patients with newly diagnosed ITP produced 100% response (platelets $>30 \times 10^9/L$) at completion of therapy, and 66.7% relapse-free survival at 1 year, better outcomes than expected for comparable patients treated with steroids alone.⁸ In a second study, 76% of steroid-nonresponsive patients had a durable response to eltrombopag after 3 months of therapy.⁹ Based on data from ICON2, pediatric hematologists are already using TPO-RAs in some cases of newly diagnosed ITP. Of 79 patients described in the ICON2 retrospective review who were prescribed a TPO-RA, 18% had newly diagnosed ITP.¹⁰ TPO-RAs may be an efficacious first-line therapy for newly diagnosed ITP patients who require treatment.

While age and duration of symptoms at diagnosis are known to predict resolution of ITP¹¹, other biologic factors that predispose some patients to resolution of their ITP and others to a more chronic course are not known. It is also not known whether the development of chronic ITP could be prevented by intervention earlier in the patient's course. A subset of patients with chronic ITP has been reported to have resolution of their disease after treatment with TPO-RAs, which was sustained after discontinuation of the medication. One postulated mechanism is immune tolerance by increasing exposure to platelet antigens, a hypothesis supported by the decreasing titer of anti-platelet antibody in one patient who resolved.¹² Another proposed mechanism is the increase in Treg functionality due to increased TGF- β 1 released by megakaryocytes.¹³ Because of the implication of Tregs in the pathogenesis of ITP and the potential immunomodulatory effects of TPO-RA, early use of eltrombopag may have an impact on the number of patients who resolve versus have persistent or chronic disease. Additionally, there are likely other biological factors which influence response to TPO-RA and other therapies that are not yet understood. Identification of these biomarkers could lead to a more personalized approach to therapy, targeted to an individual patient's disease biology.

2 STUDY RATIONALE

2.1 Study Design Rationale

Eltrombopag is an attractive option for pediatric patients needing therapy for ITP because it is an oral outpatient therapy and may have fewer side effects than standard therapies. The early response rate in this setting is not known. Pilot scale studies or observational accounts cannot answer important questions about the actual efficacy of this approach. Therefore, we have designed a randomized, two-arm, Phase 3 trial to evaluate the efficacy of eltrombopag vs. standard first-line management in pediatric patients with newly diagnosed ITP. The primary endpoint (\geq 3 of 4 platelet measurements with platelets $>50 \times 10^9/L$ at Weeks 6, 8, 10, and 12 of therapy, without rescue) is a measurable outcome clinically equivalent to the endpoint of ≥ 6 of 8 platelet measurements with platelets $>50 \times 10^9/L$ during weeks 5-12 used in a previous pediatric study of eltrombopag in chronic ITP². It is also a clinically relevant outcome in the newly diagnosed setting, as patients who are being treated because of bleeding symptoms or risk may benefit from a more sustained response during this time period, rather than repeated drops in platelet counts after transient responses to therapy.

2.3 Safety Considerations

Two pediatric trials (PETIT⁶ and PETIT2⁷) investigated the use of eltrombopag in pediatric patients aged 1-17 years with persistent or chronic ITP. The PETIT trial established dosing in an open-label dose-finding phase and then randomly assigned patients to receive eltrombopag vs placebo. 62% of patients receiving eltrombopag vs. 32% of patients receiving placebo (p=0.011) achieved the primary endpoint of platelet count $\geq 50 \times 10^9/L$ at least once in the first 6 weeks of the study without rescue. In PETIT2, 40% of patients receiving eltrombopag vs. 3% of patients receiving placebo had a sustained platelet response, with primary outcome of platelet count $\geq 50 \times 10^9/L$ during 6 of 8 of weeks 5-12 of the study.

Hepatobiliary events: Mild reversible elevations of alanine aminotransferase $\geq 3x$ ULN occurred in fewer than 10% of pediatric patients and were not associated with clinically significant symptoms. However, 3% of patients in the two studies were unable to continue eltrombopag.

Marrow fibrosis: There were no findings of bone marrow fibrosis in either pediatric trial.¹⁴

Thromboembolic events: There were no thromboembolic events in either pediatric trial.

Cataracts: In an adult randomized controlled trial (RAISE), there was no difference in cataract development between the eltrombopag group and the placebo group. In two open label studies (REPEAT and EXTEND), there was a comparable frequency of cataract incidence or progression.¹⁶ In the pediatric trials, 2 patients in PETIT2 had a cataract event (one development of a new cataract, and one progression of a pre-existing cataract).⁷ In both the adult and pediatric studies, all patients with cataract development or progression had also received corticosteroids. Current consensus among experts is that risk of cataract is not higher than baseline during eltrombopag treatment.

3 STUDY OBJECTIVES

3.1 Primary Objective

To determine if the proportion of patients with a platelet response is significantly greater in patients with newly diagnosed ITP treated with eltrombopag than those treated with standard first-line treatments

3.2 Secondary Objectives

- 3.2.1 To compare the proportion of patients with poor bleeding scores (WHO Bleeding Scale \geq 2 or Modified Buchanan Score \geq 3) at 1, 2, 3, 4, 12 weeks and 1 year in patients with newly diagnosed ITP treated with eltrombopag vs. standard first-line agents
- 3.2.2 To compare the cumulative number of rescue therapies (defined in section 8.4) needed during the first 12 weeks of treatment for patients with newly diagnosed ITP treated with eltrombopag vs. those treated with standard first-line agents
- 3.2.3 To compare platelet response during weeks 6-12 of study in patients treated with eltrombopag vs standard first line agents who required a rescue treatment during weeks 1-2 of study
- 3.2.4 To compare the proportion of patients who do not need ongoing treatment at 12 weeks and 6 months for patients with newly diagnosed ITP treated with eltrombopag vs. those treated with standard first-line agents
- 3.2.5 To compare the proportion of patients with a treatment response (4 binary endpoints (section 5.2.5)) at one year after study enrollment in patients with newly diagnosed ITP treated with eltrombopag vs. those treated with standard first-line agents
- 3.2.6 To compare the number of 2nd-line therapies (defined in section 7.2.1) used in weeks 13-52 for patients with newly diagnosed with ITP treated with eltrombopag vs. those treated with standard first-line agents
- 3.2.7 To compare the absolute change in percentage of CD4 $^{+}$ 25 $^{+}$ Foxp3 $^{+}$ regulatory T cells (Tregs) a) from baseline to 12 weeks; and b) from baseline to 1 year, in patients with newly diagnosed ITP treated with eltrombopag vs. those treated with standard first-line agents
- 3.2.8 To compare change in Health Related Quality of Life (HRQoL) from a) baseline to 1 week, b) baseline to 4 weeks, c) baseline to 12 weeks, and, d) baseline to 1 year, as measured by the parent-proxy report of the Kids ITP tools (KIT) and Global Change Scale for patients with newly diagnosed ITP treated with eltrombopag vs. those treated with standard first-line agents
- 3.2.9 To compare fatigue at 1 week, 4 weeks, 12 weeks, and 1 year as measured by the parent-proxy report of the Hockenberry Fatigue Scale-Parent (FS-P)

for patients with newly diagnosed ITP treated with eltrombopag vs. those treated with standard first-line agents

- 3.2.10 To compare iron indices at 12 weeks, 6 months, and 1 year in patients with newly diagnosed ITP treated with eltrombopag vs. those treated with standard first-line agents
- 3.2.11 Safety Evaluations: To describe the proportion of patients with abnormal liver function tests (LFTs) in patients with newly diagnosed ITP treated with eltrombopag. To describe the proportion of patients with adverse events and serious adverse events in patients with newly diagnosed ITP treated with eltrombopag and standard first-line agents

3.3 Exploratory Objectives

- 3.3.1 To compare additional platelet-defined responses in patients with newly diagnosed ITP treated with eltrombopag versus those treated with standard therapy.
- 3.3.2 To compare additional changes in HRQoL (measured by KIT) and fatigue (measured by Hockenberry Fatigue scale) at 1 week, 4 weeks, 12 weeks, and 1 year in patients with newly diagnosed ITP treated with eltrombopag versus those treated with standard therapy.
- 3.3.3 To compare cost of therapy (including medications, hospitalizations, the PROMIS survey, etc.) between patients treated with eltrombopag versus those treated with standard therapy.

4 STUDY DESIGN

This is a prospective, open label, randomized, two-arm, multi-center Phase 3 trial. Patients with newly diagnosed ITP are randomized 2:1 to receive the experimental treatment, eltrombopag, or investigator's choice of 3 standard therapies. The primary objective is to determine if the proportion of patients with platelet response is significantly greater in patients treated with eltrombopag compared to those treated with standard therapies.

Randomization at study enrollment will be stratified by the two factors described below, using a block size of 3.

- a) Age at enrollment
- b) Whether the patient has received a first-line treatment (as defined in inclusion criteria):
 - **1) Upfront treatment:** Patients *within 10 days* of ITP diagnosis who have not received previous treatment
OR
 - **2) Treatment failure:** Patients who have failed standard management (observation or treatment with one or more first-line standard agents)

Table 4A: Stratification strata and stratum-specific patient enrollment limits

Stratum	Patient Age at Enrollment	Patient Up-front Treatment Status	Maximum Number of Patients Enrolled
1	1 – <6	Requires up-front treatment	27
2	1 – <6	Failed up-front treatment	27
3	6 – <12	Requires up-front treatment	27
4	6 – <12	Failed up-front treatment	27
5	12 – <18	Requires up-front treatment	27
6	12 – <18	Failed up-front treatment	27

Patients randomized to the eltrombopag arm will be eligible to continue the treatment throughout the 1-year duration of study participation, with guidelines given for dose adjustments.

A total of up to 162 patients will be enrolled. The required sample size is 147 “informative” patients (as defined below), with 104 (estimated 98 informative) in the experimental treatment arm and 52 (estimated 49 informative) in the standard treatment arm. A conservatively high estimate of 9% of patients are anticipated to withdraw from the study prior to the 5-week platelet assessment; these patients will be classified as non-responders, and will make a non-informative contribution to the analysis response rate for the primary objective. Therefore, to obtain at least 147 informative randomized patients, we plan to enroll and randomize up to an additional 15 patients (9 and 6 for the eltrombopag and standard treatment arms, respectively) for a total of 162.

5 CRITERIA FOR EVALUATION

5.1 Primary Efficacy Endpoint

The primary endpoint is binary, with each patient classified as either a platelet responder or a platelet non-responder. Platelet responders are defined as patients with ≥ 3 of 4 platelet measurements $>50 \times 10^9/L$ between Weeks 6-12. All platelet counts will be reported, and the four measurements closest in time to Weeks 6, 8, 10, and 12 will be selected for the determination of the primary endpoint. Within a sliding one-week window, only one measurement can be selected.

Patients will be classified as non-responders for any of the following reasons:

- 1) Failing to meet the criteria to be a responder (including having an insufficient number of values $>50 \times 10^9/L$ due to missing data); or,
- 2) Requiring rescue medication at any time within the first 12 weeks of therapy; or,
- 3) Withdrawing from protocol therapy prior to week 6.

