5.2 Secondary Endpoints

- 5.2.1 Poor bleeding score (binary) at 1, 2, 3, 4 weeks, 12 weeks, and 1 year after study enrollment defined as WHO Bleeding Scale ≥ 2 or Modified Buchanan Scale ≥ 3
- 5.2.2 Cumulative number of rescue therapies required during the first 12 weeks of treatment
- 5.2.3 Platelet response (binary), defined as ≥ 3 of 4 weeks with platelets $>50 \times 10^9/L$ during weeks 6-12 of therapy, but patient required a rescue treatment during weeks 1-2 of study
- 5.2.4 No further need for treatment (binary) after 12 weeks or 6 months of study
- 5.2.5 Treatment response (binary endpoints) at 1 year defined as:
 - **CR** is defined as platelet count $>/= 150 \times 10^9/L$
 - **Primary Remission** at 1 year is defined as CR at 1 year with no second-line agents required and $>/= 3$ months after discontinuing most recent platelet active medication
 - **Disease resolution** at 1 year is defined as CR at 1 year $>/= 3$ months after discontinuing most recent platelet active medication. May have received a second-line therapy, excluding rituximab or splenectomy.
 - **Disease stability** at 1 year is defined as platelets $>/= 50 \times 10^9/L$ but $<150 \times 10^9/L$ $>/= 3$ months after discontinuing most recent platelet active medication.
- 5.2.6 Number of 2nd-line therapies (defined in section 7.2.1) in weeks 13-52
- 5.2.7 Absolute change in percentage of CD4⁺25⁺Foxp3⁺ regulatory T cells from baseline at 12 weeks and 1 year
- 5.2.8 Absolute change in parent proxy-reported KIT overall scores from baseline to 1 week, 4 weeks, 12 weeks, and 1 year after study enrollment (see Appendix A2)
- 5.2.9 Total scale intensity ratings (continuous) from the Hockenberry Fatigue Scale-Parent (FS-P) at 1 week, 4 weeks, 12 weeks, and 1 year (see Appendix A2)
- 5.2.10 Serum iron, TIBC, transferrin saturation, ferritin, MCV, and hemoglobin at 12 weeks, 6 months, and 1 year after study enrollment
- 5.2.11 Safety evaluations as defined by:
 - Abnormal LFTs:
 - ALT $\geq 3x$ ULN in patients with normal baseline
 - ALT $\geq 3x$ baseline or $\geq 5x$ ULN (whichever is lower) in patients with abnormal baseline
 - ALT $\geq 3x$ ULN AND bilirubin $\geq 1.5 \times$ ULN ($>35\%$ direct)

- Incidence of adverse events (see section 9.1.6)
- Incidence of serious adverse events (see section 12.2)

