7.2 Prohibited Medications and Treatments

7.2.1 The use of second-line platelet-enhancing therapies in weeks 1-12 is not allowed and will result in coming off protocol therapy (*i.e. subjects will discontinue eltrombopag if on study med, but subjects will continue to be followed on study for data collection*). In the event of severe or uncontrolled bleeding (Buchanan Bleeding Score of 4 or 5) requiring an emergency intervention listed below during weeks 1-12, the patient will come off protocol therapy. The following medications/procedures are prohibited during the first 12 weeks of the study:

- Dexamethasone

- Rituximab
- Mercaptopurine
- Azathioprine
- Dapsone
- Sirolimus
- Cyclosporine
- Mycophenolate
- Romiplostim
- Vinca alkaloids
- Cyclophosphamide
- Splenic artery embolization
- Splenectomy
- Other medications besides prednisone, IVIg, and anti-D thought to be active in the treatment of ITP

The use of these medications/procedures after week 12 for patients not currently taking eltrombopag (patients in the standard treatment arm, or patients in the eltrombopag arm who are non-responders and have been taken off investigational drug) is at the discretion of the treating physician, but must be reported on appropriate CRFs.

7.2.2 Other non-platelet-enhancing therapies (other than those described in section 7.1.2) are not allowed in weeks 1-12 and would be a protocol violation if used:

- Desmopressin acetate (DDAVP)
- Recombinant Factor VIIa
- Platelet transfusion

7.2.3 Patients taking anti-platelet agents (including aspirin, NSAIDs, or clopidogrel) or anticoagulants (including heparin, warfarin, or direct oral anticoagulants) are prohibited from enrolling, and these medications are not allowed during the study.

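### Could a child given a prohibited ITP therapy after the week-6 count be scored a platelet responder?

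*Combined protocol and SAP*

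**What the plan says.** Section 5.1 defines a responder by at least three of four selected counts above 50 × 10⁹/L, nearest to weeks 6, 8, 10 and 12. It lists three routes to non-response: too few qualifying counts, "Requiring rescue medication at any time within the first 12 weeks of therapy", and "Withdrawing from protocol therapy prior to week 6". Section 2.1 describes the same endpoint as counts "at Weeks 6, 8, 10, and 12 of therapy, without rescue". Section 16.b adds only a rule for missing counts.

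Section 7.2.1 lists agents and procedures barred during the first 12 weeks: "The use of second-line platelet-enhancing therapies in weeks 1-12 is not allowed and will result in coming off protocol therapy". The list ends with a catch-all, "Other medications besides prednisone, IVIg, and anti-D thought to be active in the treatment of ITP". The section foresees emergencies: for severe bleeding "requiring an emergency intervention listed below during weeks 1-12, the patient will come off protocol therapy". Follow-up continues in either case, and Section 9 confirms this for standard-arm patients who receive a prohibited therapy.

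Section 8.3 permits the three standard therapies as rescue before week 12. It calls anything beyond them additional therapy, which ends protocol therapy but not study participation. The secondary endpoints use two terms: 5.2.2 is "Cumulative number of rescue therapies required during the first 12 weeks of treatment" and 5.2.6 is "Number of 2nd-line therapies (defined in section 7.2.1) in weeks 13-52". Section 3.2.2 points to 8.4 for the definition of rescue, but 8.4 covers packaging and labelling.

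**The concern.** The primary endpoint rests on a term that Section 5.1 leaves undefined. If rescue means only the three agents permitted in 8.3, rule 2 does not reach a 7.2.1 agent. Rule 3 stops at week 6, and counts continue to be collected. A patient switched to a prohibited therapy after the week-6 count could then be called a responder to the assigned treatment, whereas a patient given a single permitted rescue course could not. The catch-all in 7.2.1 would also cover eltrombopag given to a standard-arm patient.

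The trial is open label, so an unsettled scoring rule could in principle be decided with the data in view. Cases confined to the eltrombopag arm would inflate the false-positive rate. Cases confined to the standard arm would cost power.

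**Working it through.** **Which reading the text supports**

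1. Section 8.3 begins with a functional description: patients who bleed, lose a response or never respond may need rescue. Rule 2 also speaks of *requiring* rescue. A patient who needs a 7.2.1 agent for bleeding or failure fits both.
2. Section 8.3 then says which agents may be used for that purpose. That identifies a permitted subset and does not define the whole class.
3. Section 12.1(d), on stopping treatment, speaks of rescue or ITP-directed therapy beyond what the protocol permits, cites 7.2.1 and includes emergency treatment of severe bleeding. Rescue can therefore be non-permitted.
4. Endpoints 5.2.2 and 5.2.6 differ in time window (first 12 weeks; weeks 13–52), so their different terms do not show that rescue excludes second-line agents early on. On the narrow reading, a 7.2.1 agent given in weeks 1–12 would be counted in neither endpoint.
5. The forms do not separate the classes. Section 7.3 puts any drug thought to act in ITP on the Concomitant Medications eCRF, with no exemption for the three standard agents. The rescue form also appears in the 4-month to 1-year schedule, although the three-agent permission in 8.3 applies only before week 12.

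**How narrow the literal route is**

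The patient must have used no permitted rescue and must still reach three of four counts above 50:
- switch between weeks 6 and 8: two of the three later counts if the week-6 count qualified, otherwise all three;
- switch between weeks 8 and 10: at least one earlier qualifying count;
- switch between weeks 10 and 12: at least two earlier qualifying counts.

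**Illustrative size if the literal reading were used**

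Inputs: upper boundaries *b* = 3.7103, 2.51142, 1.99302 at fractions *f* = 0.33, 0.67, 1 (Table 16A); rates 75% vs 50%; 9% non-informative, scored as non-responders; 108 vs 54 randomized (Section 16.f). The numbers of affected patients are assumed.

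Formulas, with Δ = p_E − p_S and p̄ the pooled rate:
- SE₀ = √[p̄(1 − p̄)(1/n_E + 1/n_S)]
- SE₁ = √[p_E(1 − p_E)/n_E + p_S(1 − p_S)/n_S]
- *c* = 0.5(1/n_E + 1/n_S) with continuity correction, otherwise 0
- u_k = (b_k·SE₀/√f_k + c/f_k − Δ) / (SE₁/√f_k)
- rejection probability = 1 − P(Z₁ < u₁, Z₂ < u₂, Z₃ < u₃), with corr(Z_i, Z_j) = √(f_i/f_j) for i < j

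The plan's own figure first: 98 vs 49 at 75% vs 50% gives SE₀ = 0.0825, SE₁ = 0.0838 and power 85.0% without correction, 80.3% with it, against the stated 81.4%. The corrected version is the closer, so both are shown.

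Base case: p_E = 0.75 × 0.91 = 0.6825; p_S = 0.50 × 0.91 = 0.455; Δ = 0.2275; p̄ = (108 × 0.6825 + 54 × 0.455)/162 = 0.6067; SE₀ = 0.0814; SE₁ = 0.0812. At the final look without correction, u₃ = (1.99302 × 0.0814 − 0.2275)/0.0812 ≈ −0.80. Over all three looks, power is 79.3%. The null sets both rates to 0.455.

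| Extra patients scored responder | Type I, uncorrected [corrected] | Power, uncorrected [corrected] |
|---|---|---|
| None | 2.5% [1.6%] | 79.3% [74.0%] |
| Eltrombopag 1 of 108 | 3.2% [2.1%] | – |
| Eltrombopag 2 of 108 | 4.1% [2.8%] | – |
| Eltrombopag 3 of 108 | 5.1% [3.5%] | – |
| Standard 1 of 54 | 1.5% [0.9%] | 72.4% [66.3%] |
| Standard 2 of 54 | 0.8% [0.5%] | 64.6% [58.0%] |
| Equal proportions (2/108 and 1/54) | 2.5% [1.6%] | 79.9% [74.7%] |
| One patient in each arm | 1.9% [1.2%] | 76.3% [70.6%] |

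**The case for a change.** The best case for a change is that a primary-endpoint rule should not need interpretation, least of all in an open-label trial. Section 8.3 does use a separate term for therapies beyond the three agents, and the only consequence it states is coming off protocol therapy. The protocol expects such use, both in emergencies and in the standard arm. The timing can also fit: from a 50 mg start raised at week 2, four weeks at 75 mg ends at week 6, so a stop for non-response under 8.2.2.3 is not *before* week 6 and escapes rule 3. A handful of one-sided cases would move the operating characteristics, and the remedy would be a sentence or two with no new data.

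The observation that 5.1 does not define the term in place stands, and so does the arithmetic. What does not stand is that the two readings are evenly balanced. The narrow one depends on a single change of term in 8.3 and makes a prohibited therapy score better than a permitted one, which contradicts the description of the endpoint in 2.1. The table shows sensitivity to assumed counts; it does not show a bias in this trial.

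Two related points do not alter this. The pointer from 3.2.2 to 8.4 is clerical: 8.3 is the adjacent section, carries the rescue title and is correctly cited in 7.1.1. The other is whether an early stop for a high count under Table 8B counts as withdrawing under rule 3. The table presents such stops as dose adjustment or response, and its last row provides for restarting. That reads as protocol treatment, not withdrawal.

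**Conclusion.** No change is called for. This is a gap in wording that an analyst following the plan would fill in one sensible way: an ITP-active drug or procedure given in the first 12 weeks beyond the assigned treatment, whether permitted under 8.3 or listed in 7.2.1, is rescue for rule 2 and makes the patient a non-responder in either arm. The information needed is already collected under 7.3 and on the rescue form.

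On that reading there is no effect on type I error or power, provided the assumed 75% and 50% rates carry the same meaning. The other reading would matter only if patients broke an explicit prohibition after the week-6 count, used no permitted rescue, still met three of four counts, and were concentrated in one arm. The documents give no rate for this, so neither size nor direction is established. With the continuity-corrected calculation, which is nearer the plan's stated power, a single eltrombopag-arm case leaves type I error at 2.1%, below the 2.5% allowed; two or three cases would exceed it (2.8%, 3.5%).
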